- 1) Patients with a serum creatinine greater than 2.0 mg/dl;
- 2) Patients taking medications that interfere with metabolism of rivaroxaban via CYP 3A4 inhibition.

If, after randomization, a participant is unable to take the specified medication due to financial constraints, or new information becomes available that affects the safety of the participant, the surgeon will use his/her discretion in assigning the patient to the other arm of the trial.

Participants should be withdrawn from the study if they do not receive one of the study medications at the same dosage level being studied in the trial. If a patient received a medication other than a PEPPER approved treatment group and remains on this medication, the patient should be withdrawn from the study regardless of their willingness to be followed.

Please refer to the Manual of Procedures for additional guidelines involving randomization assignments.

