In the event of the occurrence of any primary study VTE outcomes or adverse events, study medication administration will cease and subsequent management will be according to standard medical treatment and best clinical judgment of the treating physician/surgeon. Data collection on each of these patients will continue through to complete follow-up of 6 months as for all study patients. At the time of discharge, each patient will be provided with instructions and/or a prescription for the assigned anticoagulant to complete 30 days of post-operative prophylaxis per study protocol and standard practice.

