In secondary analyses, we will also perform an intention to treat analysis and an “as-treated” analysis. In the intention to treat analysis, patients will be included in the analysis in the group to which they were randomized and only be censored when they are lost to follow-up. However, some patients who are randomized will be excluded from all analyses (See sections 1.3 and 1.4 below). In the “as treated” analysis, patients will be included in the group based on the study medication they actually received. Thus, for example, if a patient is randomized to rivaroxaban but receives aspirin, they will be included in the aspirin group. This approach will include “crossover” patients and provide more precise estimates of what actually happened to patients who took the study medications, but will need to be interpreted with caution as this approach has more potential to result in a lack of representativeness of the groups.

**1.2 Treatment Comparisons.** Next, each pairwise comparison of the treatment groups (i.e., aspirin vs. rivaroxaban, aspirin vs. warfarin, rivaroxaban vs. warfarin) will be performed separately, only including those patients with no medical contra-indication for either of the two treatments in that pair. In addition, for each pairwise comparison, we will only include those patients who were randomized at sites during a period of time where patients could have been randomized to either of the two treatments being compared. For example, a patient randomized to aspirin at a site restricted to use of rivaroxaban and aspirin cannot be included in an aspirin to warfarin comparison because that patient could not have received warfarin at their respective site (see below).

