differences between groups. Therefore, similar to the estimation of risks, the primary analysis of non-inferiority will be based on only on follow-up while patients were treated with the medication to which they were randomized (a per-protocol analysis). We do recognize, however, that the exclusion or censoring of randomized patients from the analysis due to medication switching could result in differences between the groups that will bias their comparisons. To address this possibility, in secondary analyses, the patients will be weighted to adjust for imbalances between the groups with respect to age, sex, site, and education, as described in section 1.5.4 below.

The two-sided confidence interval for the treatment differences will also be used to assess superiority of one treatment over another. If the confidence interval does not overlap 0, then this would be equivalent to statistically significant superiority of one treatment over another at the two-sided 0.05-level. A p-value to summarize the strength of evidence against the null hypothesis that the risk is equal in the two groups can be calculated based on the Z-statistic:

$$= \frac{\hat{r}_{Rx1} - \hat{r}_{Rx2}}{\sqrt{VAR(\hat{r}_{Rx1}) + VAR(\hat{r}_{Rx2})}}$$

where the risks and variances are calculated using the Kaplan-Meier approach and Greenwood's formula.

Finally, comparisons of a composite of the primary effectiveness endpoint, prevention of thromboembolic events, *and* the primary safety endpoint, avoidance of bleeding-related events, will be performed among the three treatment groups. This assessment of "net clinical benefit" (Samama CM et al, NEJM 2020 May 14;382:1916-1925) will consist of comparing a combined measure, the percentage of patients with either a primary effectiveness endpoint (symptomatic DVT and PE plus all-cause mortality) or a primary safety endpoint (aggregate of bleeding complications including major, non-major clinically important, and wound-related) between each pair of treatments. Analyses will be conducted in the same manner as described above.

**1.3 Randomized patients who do not undergo surgery.** Patients who were randomized but then do not undergo surgery will be excluded from all analysis. This approach is consistent with the recommendations of Fergusson et al, BMJ. 2002 Sep 21;325(7365):652-4.

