**1.4 Study events that occur before surgery.** Outcome events that occur after randomization but before surgery will not be counted as events in this study because the study concerns post-surgery events.

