### 1.5 Additional (Secondary) analyses of the primary Aim 1.

**1.5.1 Intention to treat and as-treated analyses.** In secondary analyses, we will perform both "as treated" and "intention-to-treat" analyses. In the as-treated analysis, patients who received one of the study medications will be included in the statistical analysis in the treatment group corresponding to the treatment that they actually received. In the "intention-to-treat", patients will be included in the statistical analysis in the treatment group corresponding to the treatment to which they were randomized. The intention to treat analysis will include all randomized patients with a few exceptions (see sections 1.3 or 1.4 above). These analyses will be conducted in a manner similar to the per-protocol analysis, but including different patients and different follow-up time.

**1.5.2. Analyses aggregating those on either rivaroxaban or warfarin.** As an additional secondary analysis, we will also perform a pair-wise comparison of aspirin vs. an aggregate of patients who received either rivaroxaban or warfarin. In this analysis, we will pool the data from those who receive either rivaroxaban or warfarin. This analysis will be based on only those patients eligible for aspirin and either rivaroxaban or warfarin.

**1.5.3 Analyses based on different time periods.** In an additional secondary analysis, we will compare the treatment groups with respect to risk of events in the first 7 days post-surgery, and in the first month post-surgery.

**1.5.4 Analyses adjusting for potential confounding created by exclusion of some patients, loss to follow-up, or switching from randomized treatment.** Inevitably there will be some randomized patients who are lost to follow-up at one time or another. These patients will be censored at the time they were lost to follow-up. In addition, as mentioned above, we will censor patients when they switch from the treatment to which they were randomized, and exclude those who do not have surgery or have events before surgery. The missing or excluded data can result in imbalances between

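### Mandatory withdrawal of patients given a non-study drug or dose contradicts the secondary intention-to-treat analysis and discards outcome data that could be collected

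*Protocol*

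**What the plan says.** Protocol section 3.1.2 d) Randomization ends with two withdrawal rules for patients already randomised.

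- Dose and drug received: "Participants should be withdrawn from the study if they do not receive one of the study medications at the same dosage level being studied".
- Non-study drug: for a patient who received a drug outside the trial's treatment groups and stays on it, "the patient should be withdrawn from the study regardless of their willingness to be followed".

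The same section lets the surgeon move a patient to the other study arm after randomisation because of cost or new safety information. Those patients are not withdrawn.

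Section 3.1.3 plans ITT as a secondary analysis. Under 1.1, patients are analysed "in the group to which they were randomized and only be censored when they are lost to follow-up". Under 1.5.1: "The intention to treat analysis will include all randomized patients with a few exceptions (see sections 1.3 or 1.4 above". Those exceptions are section 1.3 ("Patients who were randomized but then do not undergo surgery will be excluded from all analysis") and section 1.4 ("Outcome events that occur after randomization but before surgery will not be counted as events in this study"). Withdrawal because of the drug or dose received is not among them.

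Section 3.1.2 e) covers patients whose study drug stops after a VTE outcome or adverse event and who are then managed by clinical judgment. For them: "Data collection on each of these patients will continue through to complete follow-up of 6 months as for all study patients".

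**The concern.** The withdrawal rules remove from follow-up some patients whom the ITT definition keeps in. The reason for removal is the treatment received after randomisation, which is what ITT is meant to disregard.

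ITT matters here although it is secondary. The primary non-inferiority analysis is per-protocol, and section 1.2 concedes that excluding or censoring switchers could bias the group comparison. ITT is the natural check on that. One of the missing-not-at-random sensitivity analyses in section 1.5.4 is itself an ITT analysis, rerun without the sites with the most cross-over, so it has the same gap.

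This is a rule about data collection, so a statistical analysis plan cannot repair it: outcomes never collected cannot be analysed. The record review in section 3.1.2 f) covers patients with events and 6-month non-responders, and the death-index search covers 6-month non-responders. Neither is stated to cover withdrawn patients.

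**Working it through.** **1. The rules side by side**

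| Patient after randomisation | 3.1.2 d) | ITT in 3.1.3 (1.1, 1.5.1) |
|---|---|---|
| No surgery | not addressed | excluded (1.3) |
| Moved to the other study arm | stays in study | included as randomised |
| Study drug not at the studied dose | withdrawn | included |
| Received and stays on a non-study drug | withdrawn, even if willing | included |

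The last two rows conflict. If the rules are followed, ITT can only censor these patients at withdrawal, using the general rule in 1.1 for incomplete follow-up. A patient on a non-study drug from the outset would contribute almost no follow-up.

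**2. Anchoring the inputs on Table 1 (aspirin vs warfarin)**

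Inputs: 4703 and 4698 eligible, cross-over 6.4% and 21.5%, 90% complete follow-up, margin 0.69 points (all Table 1); risk 1.1% (section 5.2).

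- n: 4703 × 0.936 × 0.9 = 3962; 4698 × 0.785 × 0.9 = 3319.
- SE = √[0.011 × 0.989 × (1/3962 + 1/3319)] = 0.00245.
- CI width = 2 × 1.96 × SE = 0.96 points, as stated.
- Power = Φ(0.0069/0.00245 − 1.96) = 80.3%, as stated, at one-sided 0.025.

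This confirms the 1.1% risk and the 0.69 margin as planning values. It does not measure withdrawals.

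**3. Possible effect on one arm's ITT risk (assumption only)**

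Let a share w of an arm be withdrawn before contributing events, with k times the arm's average risk of 1.1%. The risk seen in those retained is 1.1% × (1 − wk)/(1 − w). The protocol gives neither w nor k.

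| w | k | Retained risk | Understated by (points) |
|---|---|---|---|
| 2% | 2 | 1.078% | 0.02 |
| 2% | 3 | 1.055% | 0.04 |
| 5% | 2 | 1.042% | 0.06 |
| 5% | 3 | 0.984% | 0.12 |
| 10% | 2 | 0.978% | 0.12 |
| 10% | 3 | 0.856% | 0.24 |

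The extremes are 0.022/0.69 = 3% and 0.244/0.69 = 35% of the margin.

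**4. Effect on the comparison**

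Non-inferiority turns on the difference between arms. With equal true risk and the same w and k in both arms, the shift is zero. With k = 3, w = 2% on aspirin and 10% on the comparator, aspirin minus comparator shifts by 1.055 − 0.856 = +0.20 points, against a non-inferiority finding. With the two shares reversed it shifts by −0.20, towards one.

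**The case against.** Several stronger readings are tempting, and the protocol does not support them.

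- **That ITT cannot be done.** It can be run with censoring at withdrawal. What cannot be done is the analysis as 1.1 and 1.5.1 define it.
- **That the 21.5% and 6.4% in Table 1 show how many are lost.** Table 1 labels them cross-over rates, and patients who cross to the other study arm stay in the study. The 7223 in section 5.1 is no base for the count either, since it is patients assigned to and treated with rivaroxaban.
- **That the loss is known to be informative and unequal.** Section 3.1.2 d) routes cost and new safety concerns to the other study arm, which leaves a residual group whose reasons and distribution by arm are not described. Informative loss is possible but not shown.
- **That section 3.1.2 e) flatly contradicts 3.1.2 d).** Section e) concerns patients whose study drug stops after an event; d) concerns those not given a study drug at the studied dose, or staying on another drug. They may be different groups. They overlap if another anticoagulant is given after an event, and the text does not say which rule then applies.
- **That every withdrawal overrides willingness.** That phrase belongs to the non-study-drug sentence only.

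It is also fair to say that the 10% upper value in the illustration equals the protocol's whole allowance for no surgery, withdrawal and missing follow-up (Table 1, note 2), so it is an extreme case. Section 1.5.4 offers weighting and missing-data sensitivity analyses. These help, but they do not recover outcomes, and the candidate weighting variables (age, sex, site, date of surgery, education) do not directly measure clotting or bleeding risk.

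What stands is the conflict between 3.1.2 d) and the ITT definition, and the loss of data that willing patients would provide.

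**Conclusion.** The concern holds in limited form. The withdrawal rules and the ITT population are incompatible as written, and following the rules gives censoring that depends on treatment received. The weakness reaches the ITT analyses and the ITT-based sensitivity analysis in 1.5.4. The primary per-protocol analysis is little changed, because it already excludes patients not treated as randomised and censors those who switch.

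The number withdrawn is not given, so neither the size nor the direction of any bias can be derived. The range of 0.02 to 0.24 points for one arm rests wholly on the assumed 2 to 10% withdrawn and 2 to 3 times average risk, with withdrawal before any event is counted. Later withdrawal would lose less. The effect on the comparison depends on how unequal the withdrawals are, and could be nil. This should be corrected, but it does not by itself invalidate the primary analysis.

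**What to change.** Separate the end of study treatment from the end of follow-up. Replace the two withdrawal sentences in 3.1.2 d) with a statement that receipt of a non-study drug or dose ends per-protocol follow-up on that date, while the participant stays in outcome follow-up to 6 months unless consent is withdrawn. Reconcile 3.1.2 d) and e) with 1.1 and 1.5.1 of section 3.1.3, including the case where another drug is given after an event.

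For patients already withdrawn under the rule, apply the existing record review and National Death Index search where consent allows and restore them to the ITT analysis. Report the number withdrawn by arm, so that readers can judge what remains missing.

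The cost is a short amendment, some additional routine follow-up contacts, and record retrieval with a consent check at the sites for those already withdrawn. No dose or treatment rule changes.

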### e) Study Medication Administration

*Aspirin group:* Enteric coated aspirin (162 mg po) will be administered on the day of operation, prior to surgery, with a sip of water. Thereafter, starting on postoperative day #1, all patients in the aspirin group will receive 81 mg po bid to complete the treatment period of 30 days. Patients on preoperative cardiac dose aspirin may continue their usual dosing regimen prior to the morning of surgery, and then commence the PEPPER trial aspirin dose of 81 mg po bid on the day after operation.

*Rivaroxaban group:* Rivaroxaban 10 mg will be first administered approximately 24 hours after completion of the index operation. Medication will then be administered in the evening on postoperative day #2 and thereafter each evening until completion. Patients on cardiac dose aspirin may will continue their regular cardiac dose aspirin if randomized rivaroxaban. Please refer to the Manual of Procedures for specific Rivaroxaban administration timing.

*In May 2023, PCORI approved the removal of warfarin from the PEPPER trial. Warfarin medication administration guidelines will no longer apply for patients enrolled after the approval date of this protocol and subsequent site-specific IRB approvals. Dosing for those patients who have previously been randomized to warfarin prior to this protocol approval will be as follows:*

*Warfarin group:* Warfarin will be administered starting on the day of operation, prior to surgery, with a sip of water. The initial dose will be empirically determined by body weight: less than 125 lbs (56.7 kg) – 2.5 mg; 125-250 lbs (56.7-113.4 kg) – 5 mg; greater than 250 lbs (113.4 kg) – 7.5mg. The initial dose will be repeated on the evening of surgery if the preoperative dose was administered prior to noon on the day of operation; no warfarin will be given on the evening of surgery if the preoperative dose was received after noon on the day of operation. Thereafter, starting on postoperative day #1, warfarin will be given each evening based on INR values to achieve a target of 2.0 (range 1.7-2.2).

In the event of the occurrence of any primary study VTE outcomes or adverse events, study medication administration will cease and subsequent management will be according to standard medical treatment and best clinical judgment of the treating physician/surgeon. Data collection on each of these patients will continue through to complete follow-up of 6 months as for all study patients. At the time of discharge, each patient will be provided with instructions and/or a prescription for the assigned anticoagulant to complete 30 days of post-operative prophylaxis per study protocol and standard practice.

### f) Follow Up Visits

Study patients will be contacted at 4 weeks (+ 10 days), 3 months (+/- 10 days), and 6 months (+ 3 months/- 1 month) after operation through Statix, LLC, a centralized data collection group located in Salt Lake City, UT. Serial efforts

to obtain follow-up of research subjects through mail, telephone, electronic communication, and web-enabled online surveys will be conducted. Central PRO data collection personnel will interrogate for comorbidities, joint function, and general well-being information using either the hip or knee disability and osteoarthritis outcome scores (HOOS and KOOS, respectively) as well as the PROMIS-10 global health survey. Study coordinators will contact the patient and inquire about and confirm any known or suspected VTE outcomes or adverse events reported by the patient by either verification of the local medical record or obtaining the medical record from the outlying facility where the patient was treated. Specifically, readmission to outside hospitals will be confirmed by record retrieval and review by the site coordinator at the study site where the index procedure was performed.

Our experience is that patient reporting of *events* increases yield of data collection; since 1 in 4 readmissions go to facilities other than that of the index procedure, observed *plus* patient reported readmissions will be captured. All centrally identified clinical study endpoint events that are confirmed by on-site coordinator record review and patient interview, will then be adjudicated by an expert panel (Outcomes Assessment Committee; OAC).

In the event that a patient has not been reached to complete the follow-up assessments, the study coordinator will contact the patient or present to the follow up clinic visit to facilitate completion of the surveys with the patient.

Medical record review will be performed on all participants who experience either endpoint events or adverse events (either reported by the patient during follow-ups or following *ad hoc* discovery by site coordinators), and those who fail to otherwise respond to data collection efforts at the 6-month follow up.

A search of the National Death Index will be performed on those patients who have failed to respond to the 6 month follow up and who have not been reported as deceased by any other measure. In order to collect data on any possible deaths, patient identifiers already collected for the PEPPER trial will be submitted to the National Death Index. The National Death Index will perform a cause of death retrieval report for any and all causes of death where applicable. Patient identifiers and subsequent death information will be submitted and shared via a secure SFTP server.

For those sites that have larger populations of Spanish speaking patients, follow up interviews will be conducted by Statix in Spanish. All study documents, including the consent document, HIPAA authorization form, and any paper-based assessments will be appropriately translated and submitted for IRB approval before any Spanish speaking patients are enrolled.

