### 1.1. Primary Aims

The Primary Specific Aims of the research are:

1) To compare the frequency of the aggregate primary clinical endpoints of important venous thromboembolism (clinical PE and DVT leading to hospital readmission) and all-cause mortality (aggregate indicator of fatal events, including both PE and major hemorrhage related to anticoagulant use) among three different venous thromboembolism (VTE) prophylaxis regimens. An audit of all hospital readmissions within 6 months of operation will be accomplished by routine postoperative follow-up through a mechanism of central telephone surveillance of patient-reported outcome events that is augmented by on-site research coordinator follow-up and validation of suspected endpoint events and adverse outcomes.

2) To compare the frequency and nature of bleeding complications (major, clinically important, and wound-related) leading to wound drainage, reoperation, deep infection, or myocardial infarction among three different VTE prophylaxis regimens. Bleeding complications are defined below and will be weighted relative to other events by the Patient Advisory Board.

3) To compare the groups with respect to patient-reported outcomes in order to assess their impact on specific function of the replaced joint as well as general patient well-being. Validated functional outcome tools will be compared among patients with and without primary endpoint events, as well as with historical baseline data warehoused in the FORCE registry, a national AHRQ funded joint replacement outcomes database. Study site overlap with the FORCE registry is planned.

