#### d) Randomization

Randomization of consented patients occurs after the surgeon confirms eligibility and up until the day before the originally scheduled surgery date. If a patient's surgery is postponed, or cancelled and ultimately rescheduled, the patient will keep the original randomization assignment. The ability to randomize a patient will be available via the web-based randomization system once consent has been signed and all baseline instruments have been entered into the database. Study group assignments will be shared with the surgeon at the time of randomization, and with the patient on the day of operation unless necessary to provide third party insurance coverage for prescribed medical care.

Patients will be assigned to treatment groups using a web-based randomization system. A permuted block randomization scheme will be utilized to ensure equal assignment of patients to each drug study group at each participating site, taking into consideration the noted criteria for stratified randomization. In the absence of any randomization stratification requirements, patients meeting all eligibility criteria without any randomization exclusions will be assigned to one of two groups; a concealed centralized randomization schedule will provide assignment to one of two prophylaxis regimens (aspirin or rivaroxaban) in randomly varying block sizes developed separately for each clinical site and stratified according to type of surgery (hip or knee replacement). Prophylaxis will continue for 30 days, in accordance with clinical guidelines, and pneumatic compression devices will be utilized in hospital in conjunction with both of the treatment groups according to local practice. The two groups are as follows:

- 1) Enteric coated aspirin (regimen with lowest bleeding risk; clinical PE and all-cause mortality rates comparable to more intensive anticoagulants); and
- 2) Rivaroxaban, an oral direct Factor Xa inhibitor (regimen with lowest PE and DVT rate but higher bleeding risk [3-5%]).

A contraindication to one of the two study prophylaxis regimens for venous thromboembolism is exclusionary. The contraindications to aspirin are:

- 1) Patients with a known aspirin allergy;
- 2) Patients with a personal history of PE or DVT;

- 3) Patients with a known condition of thrombophilia proven by diagnostic testing; e.g. Factor V Leiden;
- 4) Patients with a cancer diagnosis who are under active treatment.

The contraindications to rivaroxaban are:

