## 3.1.3. Data Analysis

Primary Data Analysis

The unblinded nature of the clinical trial could threaten unbiased comparisons. Randomized patients will not be notified of treatment group assignment until the day of the proposed operation, unless necessary to provide third party insurance coverage for prescribed medical care. Further, our trial is protected from this threat to adherence with treatment assignment by the short course of treatment, the follow-up contact to ascertain treatment, and the motivation of each patient to take prescribed drugs to prevent PE and DVT. The trial is protected from the threat to unbiased outcome ascertainment and classification by the independent centralized contact with patients to determine need for collection of clinical documents, preparation of documents related to readmission or treatment for bleeding or thrombosis to remove any indication of treatment assignment, and blinded outcome classification based upon expert review of the redacted documents by the OAC.

**1.0 Primary Aim 1.** *To compare the frequency of the aggregate clinical endpoint of important venous thromboembolism (clinical PE and DVT leading to hospital readmission) and all-cause mortality.*

**1.1 Risk Estimates.** First, 6-month probabilities of our primary composite endpoint (clinical PE, clinical DVT, and all-cause mortality) by treatment group will be estimated and compared. To address the fact that some participants will have incomplete follow-up (e.g., we may know whether they had an event within 3 months but not for the full 6 months), we will estimate 6-month risk of an event using a Kaplan-Meier approach. Confidence intervals will be based on Greenwood's formula (applied using the delta method to a complementary log-log transformation of the estimated risk). In these calculations, those whose follow-up is incomplete will be censored at the time that the follow-up ends.

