### Missing Data

A high retention rate of enrolled participants is critical to the internal and external validity of a randomized clinical trial. Patients who are more difficult to locate or are less cooperative in follow-up participation generally have lower social and residential stability, poorer treatment outcomes, and are more likely to experience financial, marital

status, and occupational changes. Many of these same factors are also well known to contribute to differences in health outcomes, health disparities, and healthcare utilization differences. To minimize non-response and loss to follow-up bias, we will rely on independent established third party data collectors who will devote considerable levels of charted effort to follow-up data collection. This approach to centralized data collection will ensure serial efforts to obtain follow-up of research subjects through mail, telephone, electronic communication, and web-enabled online surveys. It will incorporate a 1-800 message, fax and e-mail options for participant convenience, and use postage-paid reply mail service, address forwarding, and multiple efforts in multiple formats to locate patients whose addresses, phone numbers or e-mail become insufficient. Participants will be provided online accounts to complete required surveys. Our centralized data collection center will not have access to randomization assignments in order to minimize bias in data collection. An outcomes assessment committee will blindly review all adverse event reports. Despite rigorous efforts to minimize missing data or outcome information, inevitably there will be some patients with missing outcome information. We will use the methods described above to mitigate biases due to missing data, or to assess the sensitivity of our results to assumptions about missing data.

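### Site-coordinator confirmation comes before blinded adjudication, and the protocol does not reconcile this with its statement that all adverse event reports are reviewed blind or with its claimed protection against biased ascertainment

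*Protocol*

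**What the plan says.** - **Order of steps.** Protocol 3.1.2 f) has the central data collector contact patients. Then: "Study coordinators will contact the patient and inquire about and confirm any known or suspected VTE outcomes or adverse events reported by the patient". Centrally identified endpoint events "that are confirmed by on-site coordinator record review and patient interview, will then be adjudicated by an expert panel", the Outcomes Assessment Committee (OAC). Section 1.1 describes the same role: central surveillance is "augmented by on-site research coordinator follow-up and validation of suspected endpoint events and adverse outcomes".
- **Who knows the assignment.** Section 3.1.2 d): "Study group assignments will be shared with the surgeon at the time of randomization, and with the patient on the day of operation", with an exception for insurance coverage. The Missing Data section says the central collector has no access to assignments. No section says this of coordinators.
- **What is claimed.** Section 3.1.3 opens: "The unblinded nature of the clinical trial could threaten unbiased comparisons". It then argues that ascertainment is protected by independent central contact, by redaction of documents and by "blinded outcome classification based upon expert review of the redacted documents by the OAC". The Missing Data section adds: "An outcomes assessment committee will blindly review all adverse event reports". Section 3.1.2 g) has all endpoints adjudicated by committee members unaware of group.

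**The concern.** As 3.1.2 f) is written, the last judgment before blinded review is made at the site. The committee can reject a confirmed event that does not meet the definition. For an event that was reported but not confirmed, this section gives it nothing to review. If confirmation depended on the known drug, blinding further down the line would not repair it.

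The primary endpoint is rare and its margin is an absolute difference, so a small difference in confirmation between arms passes straight into the estimate. The Aim 2 endpoints leave more room for judgment. Persistent drainage beyond 5 days needs no imaging, and the protocol itself sets expectations by arm: section 4.1.3 puts reoperation for bleeding at 0.2% on aspirin and 5.0% on rivaroxaban. Bleeding also enters the net clinical benefit comparison in 3.1.3, item 1.2.

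**Working it through.** **1. The passages side by side**

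| Section | What reaches the OAC | Coordinator step mentioned? |
|---|---|---|
| 3.1.2 f) | Centrally identified endpoint events that the coordinator has confirmed | Yes, as a precondition |
| 3.1.2 g) | All endpoints | No |
| 3.1.3, opening | Redacted readmission and treatment documents; central contact decides whether they are needed | No |
| Missing Data | All adverse event reports | No |
| 5, Research Team | Blinded site reports | Sites submit; no filter described |

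The rows differ in which events the committee sees. They do not differ on whether its review is blind.

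**2. Are coordinators blinded?** The protocol does not say. That they are not is an inference from three facts: they interview patients who know their drug; they read local and outside records; and 3.1.3 plans to redact records before committee review, so the source documents can reveal treatment.

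**3. Room for judgment, by endpoint**
- *Death:* little. The National Death Index is also searched for 6-month non-responders not already reported dead.
- *PE and DVT:* limited. Imaging and readmission are required. The coordinator still retrieves and reviews outside records, and 3.1.2 f) says 1 in 4 readmissions go to another facility.
- *Bleeding and wound drainage:* most. Drainage has no imaging criterion.

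**4. The plan's own figure.** Table 1 (aspirin 3962, warfarin 3319, margin 0.69 points) reproduces at the 1.1% risk of item 5.2:
- SE = sqrt(0.011 × 0.989 × (1/3962 + 1/3319)) = 0.245 points
- CI width = 2 × 1.96 × 0.245 = 0.96 points (stated 0.96)
- power = Φ(0.69/0.245 − 1.96) = 80.3% (stated 80.3%)

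The concern changes none of these. They only give the scale.

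**5. Illustration: loss of primary events in one arm.** The loss rates are assumptions; the protocol gives no confirmation rate. Shift = loss rate × 1.1 points.

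| Loss in one arm | Shift (points) | Share of 0.69 margin |
|---|---|---|
| 5% | 0.055 | 8% |
| 10% | 0.11 | 16% |
| 20% | 0.22 | 32% |

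For aspirin against rivaroxaban, the margins of error in item 5.2 (0.27 and 0.30 points) imply n = 1.96² × 0.011 × 0.989 / 0.0027² = 5733 and, with 0.0030, 4644. Then SE = sqrt(0.011 × 0.989 × (1/5733 + 1/4644)) = 0.206 points, so a shift of 0.11 is about half a standard error.

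**6. Illustration: error rate at the margin.** Take Table 1 numbers and true risks of 1.79% (aspirin) and 1.10%. Suppose a share of aspirin VTE events is lost in that arm only. The share of primary events that are VTE is not given, so two values are shown.

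| Loss | Half of events VTE | All events VTE |
|---|---|---|
| 0% | 0.025 | 0.025 |
| 5% | 0.036 | 0.051 |
| 10% | 0.051 | 0.097 |
| 20% | 0.097 | 0.277 |

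An equal 10% loss of all events in both arms gives 0.045, because it shrinks an absolute difference. Loss in the comparator arm alone would work against aspirin.

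**The case against.** The strongest reply is that the step is ordinary source verification. Section 3.1.2 f) describes confirming as checking the local record or obtaining the outside one, which is largely retrieval. Record review is required for every participant with a reported or discovered event and for 6-month non-responders. No rule tells coordinators to discard a report. This stands in part: the text can be read that way, but it does not say so, and the adjudication sentence makes confirmation a condition. The record review is not assigned to anyone blinded.

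A reader might infer that nothing unconfirmed can ever reach the committee. The documents do not support that. Section 4.1.3 counts any death, unplanned readmission or reoperation on the index joint as a serious adverse event. Section 4.5 plans narratives of each such event, organized through what is presumably the same committee. This may be a second route. The protocol does not say whether those narratives come from the same coordinators or feed endpoint classification.

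A reader might also infer a flat contradiction. All endpoints and all adverse event reports can be read as all those that sites submit, so this is a mismatch of scope. Nor does the protocol state that coordinators are unblinded; only the surgeon and the patient are named as being told the assignment.

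Finally, the primary endpoint leaves little discretion, and the protocol offers no reason why imaging-proven VTE would be confirmed differently by arm. That limits the concern for Aim 1. It does not answer it for Aim 2.

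**Conclusion.** The concern holds as an unreconciled step. Section 3.1.2 f) places confirmation, by staff who are not stated to be blinded and very likely are not, ahead of blinded adjudication of centrally identified events. The Missing Data section and the protection argument in 3.1.3 do not account for it.

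Its size and direction are unknown. The figure of 0.11 points for a 10% one-arm loss applies the loss to all primary events, deaths included, so it overstates what a filter on VTE reports alone would do at that rate. A reader might infer that the non-inferiority result is compromised. Nothing in the protocol shows that any event has been lost, or that confirmation differs by arm. The correction is worth making because it is cheap, and because the softer safety endpoints lack the safeguards that death and imaging give the primary one.

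**What to change.** Amend 3.1.2 f) so that coordinator confirmation means retrieving documents, not deciding whether an event is eligible for adjudication. From now on, suspected PE or DVT, bleeding, wound-drainage, reoperation and infection reports go to the existing committee as redacted packets, including those judged not confirmed. Align 3.1.2 f), the opening of 3.1.3 and the Missing Data section.

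At a minimum, log each unconfirmed report with its reason, tabulate these by arm, and send the unconfirmed VTE reports for blinded review.

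**Cost.** The cost is reviewer time. No new committee is needed, and treatment, sample size and the primary analysis are unaffected. Assume one to two unconfirmed reports per true event:
- Primary events: 1.1% × 18,000 = 198, so about 200 to 400 packets.
- Bleeding, at the midpoint rates of item 5.2 and the group sizes of item 5.1: 7223 × 4.5% + 7239 × 0.75% + 5389 × 1.5% = 325 + 54 + 81 = 460, so about 460 to 920 packets.
- Together: about 660 to 1,320 over the whole trial.

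A change applied only from now on would generate fewer, since 5132 + 5389 = 10,521 patients had been randomized to aspirin or warfarin by May 2023. The minimum version needs fewer again, at most the 200 to 400 of the first line, which still includes deaths.
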